5.6. Number of Subjects

The study is designed to report on 20 subjects who receive a Gemini SCS implant and complete follow-up. [REDACTED]

5.7. Total Expected Duration of the Clinical Investigation

Subjects participating in this clinical investigation will be followed for approximately 6 weeks after the permanent implant procedure. [REDACTED]

6. TREATMENT AND EVALUATION OF ENDPOINTS

6.1. Baseline/Pre-procedure

6.1.1. Baseline Assessments

Baseline visit should occur no more than 15 days after enrollment. If an SCS trial was performed, baseline pain and functional assessments should be made after at least 5 days without stimulation. If it is not possible to have stimulation off for at least 5 days, baseline data may be obtained from medical records from the last 6 months. The baseline pain score reported should be the score used to evaluate the inclusion and exclusion criteria (no stimulation NRS \geq 6, stimulation NRS \leq 4). The following baseline data will be collected:

- Patient demographics
- Pain diagnosis (specifically the subject's primary indication for neuromodulation) and pain location
- Pain history (time with chronic pain, previous treatment)
- Prior interventions (e.g. physical therapy, injections, surgeries) to treat the presenting condition
- Numeric Rating Scale (NRS) for pain intensity
- PROMIS-29
- Adverse events (if applicable)

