5.3.2. Inclusion Criteria

1. Subject is indicated for an SCS system, or has an implanted SCS system and is scheduled to receive an IPG replacement.
2. Subject is scheduled to receive a new IPG permanent implant and has completed a successful SCS trial in the last 6-months, OR subject is scheduled to undergo an all-in-one procedure OR has an implanted SCS system for an approved chronic pain indication.
3. Subject has a documented NRS pain score of ≥ 6 after at least 5 days without stimulation OR has an implanted functioning SCS system with NRS pain score of ≤ 4 .
4. Subject must provide written informed consent prior to any clinical investigation-related procedure.
5. Subject is at least 18 years at the time of enrollment.
6. Subject is capable and willing to recharge an implanted IPG.

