6.3.3.1. Pain Numerical Rating Score (NRS)

The pain NRS consists of 1 question that will be asked by interviewing the subjects. Patients will be asked to rate, from 0 (no pain) to 10 (worst imaginable pain), their pain at the time of study visit specific to the area(s) of chronic pain being treated. A higher score indicates greater pain intensity.

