6.3.3.2. Patient-Reported Outcome Measure Information System (PROMIS-29)

The PROMIS-29 is an adult scale developed in partnership with the National Institutes of Health (NIH) in the United States to estimate overall quality of life by assessing the following domains known to impact activities of daily living: physical function, sleep disturbance, depression, anxiety, fatigue, pain interference, pain intensity, and social role satisfaction. The scale requires subjects to rate the frequency and/or severity of symptoms and experiences related to each of these domains. A total score is calculated and transformed against normative data into a t score indicating global quality of life in relation to population norms. Subscales are defined by each domain described above and can be examined separately to parse separate symptoms or deficiencies in quality of life. The final item is an 11-point pain intensity numerical rating scale (NRS) by which the subject rates their average pain over the past 7 days. Subjects should read each item and check the one box that most closely represents their response.

Clinical Investigation Plan

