3.4 Descriptive Performance Endpoints or Additional Data

Descriptive Endpoints

The descriptive endpoints will be analyzed using the methods defined in 2.2 based on implanted population defined in 2.1. The descriptive endpoints will be analyzed at baseline and at 6 weeks if applicable.

Descriptive endpoints include:

- Patient satisfaction
- Patient experience with charging
- NRS score change
- PROMIS-29 change
- Charging history

The following charging history will be summarized using the methods defined in 2.2

- Time between implant and first charging session in days
- Number of charging sessions
- The rate of charging sessions per follow-up week
The numerator will be the total number of charging sessions. The denominator will be the total follow-up duration (in weeks) from the date of first charging started to the last follow-up date
- Average duration of charging (in hours) per charging session
- Average charging interruptions per charging session
- Rate of charging sessions with Overheat protection events, which is defined as total number of sessions with overheating protection flag/total number of charging sessions
- The average percent of battery at end of the charging sessions per charging session

- Stimulation programs used
- Stimulation programs available

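### The reported baseline NRS is to be the score that qualified the subject, so the descriptive 6-week NRS change carries regression to the mean, in opposite directions for the two eligibility routes

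*Protocol*

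**What the plan says.** Inclusion criterion 3 (Protocol 5.3.2) has two routes. The first reads "Subject has a documented NRS pain score of ≥ 6 after at least 5 days without stimulation". The second reads "OR has an implanted functioning SCS system with NRS pain score of ≤ 4".

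Protocol 6.1.1 ties the baseline to that criterion: "The baseline pain score reported should be the score used to evaluate the inclusion and exclusion criteria". It repeats both cut-offs. It also gives a fallback: "If it is not possible to have stimulation off for at least 5 days", then "baseline data may be obtained from medical records from the last 6 months".

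Protocol 6.3.3.1 says that the NRS asks subjects to rate "their pain at the time of study visit specific to the area(s) of chronic pain being treated". The schedule of events (Protocol 6.3.5) places the NRS and PROMIS-29 at baseline and at 6 weeks. Protocol 3.1 allows enrollment, baseline and implant on the same day.

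Protocol 4.2 lists NRS change under additional data, below the two additional safety endpoints. SAP 3.4 lists "NRS score change" among the descriptive endpoints. SAP 2.2.1 summarizes differences from baseline to 6 weeks, where specified, by a mean and a 95% confidence interval. Neither SAP section separates the eligibility routes or the baseline sources.

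**The concern.** A score that had to pass a threshold is, on average, more extreme than the same subject's usual level. If it also serves as the baseline for change, the next measurement drifts back with no help from the device. Subjects admitted at 6 or above would appear to improve, and subjects admitted at 4 or below would appear to worsen. The study has no control arm in which to see that drift.

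Three further mixtures sit in the same mean:

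- **Stimulation state.** The first route compares a stimulation-off baseline with a follow-up after the new system has been activated. The second compares stimulation-on with stimulation-on. These are different quantities.
- **Source.** A chart score was not necessarily obtained by the study's own question about pain at the visit. Sections 6.1.1 and 6.3.3.1 need to be reconciled on this.
- **Date.** A chart baseline can be much older than a visit baseline.

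What is at stake is how the reported pain change is read. Protocol 15.1 names reduced perceived pain as an expected benefit, and NRS change is the direct measure of it.

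**Working it through.** The visible text gives no NRS effect size, SD or power, so there is no plan figure to reproduce. The check covers timing and the expected change when the device has no effect.

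**Timing (from the stated windows).** Implant is at most 60 days after enrollment, and the 6-week visit is 30 to 45 days after implant. Six months is taken as 183 days.

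- Chart baseline to 6-week NRS: up to 183 + 60 + 45 = 288 days if the 6 months count back from enrollment. If they count back from a baseline visit on day 15, the maximum is 288 − 15 = 273 days.
- Baseline-visit NRS to 6-week NRS: 30 days (all on one day) to 60 + 45 = 105 days.

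**Regression to the mean.** For selection above a cut-off c, the expected no-effect change is −(1 − r) × SD × φ(a) / (1 − Φ(a)), with a = (c − mean) / SD. Selection below a cut-off is the mirror image with positive sign. For whole-number scores, c = 5.5 represents 6 or above and c = 4.5 represents 4 or below. The means, SDs and test-retest correlations r are assumptions; the documents give none.

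- Mean 6, SD 2: a = −0.25, and the selected mean is 7.29, an excess of 1.29. The change is 0.5 × 1.29 = 0.65 points at r = 0.5 and 0.2 × 1.29 = 0.26 at r = 0.8.
- Mean 7, SD 1.5: a = −1, an excess of 0.43. The change is 0.22 at r = 0.5 and 0.09 at r = 0.8.
- Route at 4 or below: means of 4 and 3 with the same SDs give the same sizes, upward.

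Simulation of whole-number 0 to 10 scores (1,000,000 draws) gave 0.10 to 0.67 in each direction. Wider assumptions were also tried: means 6 to 7.5 or 3 to 4.5, r up to 0.9, and the cut-off at the whole number or half a point beyond it. These give a fall of 0.03 to 0.8 and a rise of 0.04 to 0.96.

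**Pooled mean** (simulated; means 6.5 and 3.5, SD 2, r = 0.6), by share entering through the route at 6 or above:

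| Share | No-effect change |
|---|---|
| 100% | −0.43 |
| 75% | −0.22 |
| 50% | about 0 |
| 25% | +0.22 |

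**Scale.** With 20 subjects the 95% half-width is 2.093 × SD / √20. That is 0.70, 0.94 or 1.17 for an assumed SD of change of 1.5, 2.0 or 2.5.

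**Effect of a separate baseline score.** In simulation with r = 0.6, a second score taken after selection and used as baseline moved the no-effect change from −0.19 to 0.00 (mean 7, SD 1.5) and from −0.43 to 0.00 (mean 6.5, SD 2). The mirrored route gave the same result with opposite sign. This needs the second score to be no more closely tied to the qualifying score than the follow-up score is.

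If a same-day repeat correlates with the qualifying score at an assumed 0.9, against 0.6 for the follow-up, the remaining bias is (0.9 − 0.6) times the excess instead of (1 − 0.6) times it. That leaves 0.3 / 0.4 = 75%. For mean 6.5 and SD 2 the excess is 1.02, so about 0.31 of 0.41 points would remain by the formula.

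**The case against.** The strongest reply has four parts.

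**Wording.** The baseline rule says should, not must, and the chart route applies only when stimulation cannot be off for 5 days. A reader might infer that the protocol compels the qualifying score in every case, or freely permits old chart values. The text supports neither. The look-back also matches the 6-month window for a successful trial in inclusion criterion 2, so it may be a deliberate way to reach a pre-trial score. All of this stands. It limits how many subjects have chart baselines, but a site that follows the rule as written still builds the bias in.

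**Status.** NRS change is additional, descriptive data with no hypothesis test or visible threshold, and the study's focus is charging-related safety. This stands, and it keeps the point modest. A mean with a confidence interval is still reported, and an interval centred on a shifted mean does not allow for the shift.

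**Remedy.** Taking a new visit score as baseline for everyone looks like the obvious cure. For fallback subjects, however, it would put a score under stimulation, or soon after it, in place of a stimulation-off reference. The two cut-offs are 6 − 4 = 2 points apart, more than the bias being removed. Same-day visits also weaken the repeat. Both points stand and shape the fix.

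**Size.** It rests on assumptions, is near zero in an even mix, and stays below the half-widths above at 0.65 points. This stands too, but cancellation in a pooled mean depends on the mix of subjects and hides opposite errors in the two routes.

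The PROMIS-29 pain item, on which "the subject rates their average pain over the past 7 days", might be taken as a clean check. It is not: it is correlated with the selected NRS, its recall can reach back before a 5-day period without stimulation, and the chart fallback covers baseline data generally.

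**Conclusion.** The point holds as a modest defect in a descriptive analysis. The baseline rule makes the 6-week NRS change carry regression to the mean of about 0.1 to 0.65 points, downward in the route at 6 or above and upward in the route at 4 or below. That range assumes means of 6 to 7 or 3 to 4, SDs of 1.5 to 2 and correlations of 0.5 to 0.8. The pooled figure can fall anywhere between the two, and it blends stimulation states and baseline sources. The error added by chart age cannot be sized from the documents.

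A reader might infer that a large fall in NRS could be explained away, or that the study's main conclusion is in doubt. Neither follows: the artefact is probably under 1 point, and the confirmatory safety endpoint does not use the NRS. Nor do the documents say that NRS change will be read as a device effect; they lack a statement that it should not be. The change is worth making because it is cheap and removes or exposes a bias that the plan's own rule creates.

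**What to change.** 1. **Protocol 6.1.1.** Keep the qualifying score for eligibility. Where the baseline visit can be done in the same stimulation state as the qualifying score, ask the NRS again and use that answer as the baseline for change. Note that a same-day repeat removes only part of the bias. Reconcile the section with 6.3.3.1.
2. **Chart fallback.** Keep the chart value for these subjects, but do not pool it with visit-collected baselines.
3. **CRF.** Record date, source (visit or chart) and stimulation status for every baseline NRS and PROMIS-29 value.
4. **SAP 3.4.** Report NRS change separately by eligibility route and by baseline source. State that the uncontrolled change is not an estimate of device effect. The PROMIS-29 pain item may be shown beside it, labelled as a partial check.

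None of this alters eligibility, the period without stimulation, or treatment. The cost is one question at a visit that already schedules the NRS, a few CRF fields and extra table rows. The statistical price is wider intervals. With an assumed SD of change of 2 and an even split by route, the half-width goes from 0.94 with 20 subjects to 2.262 × 2 / √10 = 1.43 with 10 per row, and rows by source would be smaller still.

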6.2. Permanent System Implant

Implantation of the neurostimulation system will be performed according to the sites standard operating procedures and should be consistent with instructions in the IFU. It should be performed after the baseline assessments and no later than 60 days from the enrollment visit. If it has not occurred within 60 days after Enrollment, the subject will be withdrawn (Section 5.5). Following system implantation, the stimulator will be activated and programmed by trained personnel either during post-operative recovery or at an office visit in accordance with the physician's and hospital's standard operating procedures. The subject's spinal cord stimulator will be programmed according to the most recent Abbott programming guidance. After programming, the subject will receive a patient programmer and will be instructed on how to use the system to relieve their pain.

The investigator or delegate will instruct the subject on use of the charger, including weekly charging after the initial wound healing period.

Clinical Investigation Plan

A charging plan for the patient should satisfy the following criteria:

- First battery charge prior to attending the 2-week follow up visit
- Weekly battery charge after 2 weeks

The following information will be collected at the permanent system implant:

- Neurostimulation system device information
- Lead type(s) and location
- Programming parameters subject is using at the end of device activation
- All serious adverse events including deaths (if applicable)
- Non-serious adverse events related to device, procedure, stimulation, charging, or MRI (if applicable)
- Withdrawal (if applicable)
- Device deficiency (if applicable)
- Additional Surgery (if applicable)

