6.3. Follow-up Assessments

6.3.1. 2-Week Follow-up (In-Person, Phone Call or Telehealth Visit)

A 2-week follow-up visit, which may occur in person, by telephone or as a telehealth visit, will occur 10-14 days after permanent implant. The 2-week follow-up visit provides an opportunity for the site to confirm that the patient understands the charging plan and has the opportunity to report any adverse events. If the clinician programmer is connected to the subject's IPG all reports will be downloaded. The following data will be collected:

- All serious adverse events including deaths (if applicable)
- Non-serious adverse events related to device/procedure/stimulation/charging/MRI (if applicable)
- Charging history (if applicable)
- Stimulation programs used since permanent implant (if applicable)
- Stimulation programs available at the end of the visit (if applicable)
- Withdrawal (if applicable)
- Device Deficiency (if applicable)
- Additional Surgery (if applicable)

6.3.2. 6-Week Follow-up (In-Person Visit)

Subjects will be followed at a 6-week follow-up visit that will occur 30-45 days after permanent implant. The following data will be collected:

- All serious adverse events including deaths (if applicable)
- Non-serious adverse events related to device, procedure, stimulation, charging, or MRI (if applicable)

Clinical Investigation Plan

- NRS
- PROMIS-29
- Patient satisfaction
- Patient charging experience
- Charging history
- Stimulation programs used since permanent implant
- Stimulation programs available at the end of the visit
- Withdrawal (if applicable)
- Device Deficiency (if applicable)
- Additional Surgery (if applicable)

During the 6-week follow-up visit, site personnel will connect to the subject's IPG using the CP. Site personnel will use the CP to collect the charging history, programming and program use details as PDF files.

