15.2. Foreseeable Adverse Events and Anticipated Adverse Device Effects

Risks associated with the specified device and procedure, together with their likely incidence, are described in the IB/IFU. There may be risks related to the device under investigation that are unknown at present. Likewise, the exact frequency of the risk is unknown.

The use of a neurostimulation system involves risks. In addition to the risks commonly associated with surgery, below are listed the anticipated potential adverse effects with the use of a neurostimulation system:

- Unpleasant sensations or motor disturbances, including involuntary movement, caused by stimulation at high outputs (if either occurs, turn off your EPG/IPG immediately)
- Undesirable changes in stimulation, which may be related to cellular changes in tissue around the electrodes, or changes in electrode position relative to the spinal cord
- Changes in stimulation or reduced pain relief due to lose electrical connections
- Changes in stimulation or reduced pain relief due to lead failure.
- Stimulation in unwanted places such as the ribs or chest
- Changes in stimulation or reduced pain relief due to lead migration
- Epidural hemorrhage
- Hematoma
- Infection
- Spinal cord compression
- Paralysis from placement of a lead in the epidural space
- Cerebrospinal fluid (CSF) leakage
- Paralysis below the level of implant
- Weakness below the level of implant
- Clumsiness below the level of implant
- Numbness below the level of implant
- Pain below the level of implant
- Persistent pain at the lead site
- Persistent pain at the IPG site
- Seroma (mass or swelling) at the IPG site
- Seroma at the lead incision site
- Allergic or rejection response to device/implant materials
- Implant migration

Clinical Investigation Plan

- Skin erosion around the implant
- Loss of stimulation due to premature battery depletion or battery failure

The following potential adverse events may be associated with charging the system and are listed as warnings or precautions in the IFU:

- Heating or discomfort at surgical staples while recharging. Charging should not be carried out while staples are in place
- Heating or discomfort at the pocket while recharging
- Interference with another implanted medical device

The following potential adverse events may occur in the MRI environment:

- Lead electrode heating resulting in tissue damage or serious patient injury

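### For a subject still stapled when the first charge falls due, the charging plan in CIP 6.2 and the staple warning in CIP 15.2 cannot both be followed; the sections should be reconciled.

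*Protocol*

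**What the plan says.** CIP 6.2 (Permanent System Implant) introduces the charging plan with "A charging plan for the patient should satisfy the following criteria" and gives two criteria: "First battery charge prior to attending the 2-week follow up visit" and "Weekly battery charge after 2 weeks". Just before that, the same section says: "The investigator or delegate will instruct the subject on use of the charger, including weekly charging after the initial wound healing period".

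CIP 6.3.1 describes the 2-week visit as one "which may occur in person, by telephone or as a telehealth visit, will occur 10-14 days after permanent implant". Its stated purposes are to confirm that the charging plan is understood and to allow adverse events to be reported.

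CIP 15.2 lists heating or discomfort at surgical staples among the potential adverse events of charging, and adds: "Charging should not be carried out while staples are in place". It attributes these items to the warnings and precautions in the IFU.

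**The concern.** The first charge has a latest time but no condition on the state of the wound. The warning in CIP 15.2 is exactly such a condition. The two are written in different parts of the CIP without a cross-reference, and the first charge is due early, before the period of weekly charging that CIP 6.2 links to wound healing.

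Three things are at stake.

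- **Subject safety.** CIP 1.1.2 says that the study concentrates on events that could be due to the new charging system. A site that follows the charging-plan criterion literally could act against the CIP's own warning about that component.
- **Deviation handling.** CIP 10.6 grants no waivers and requires every deviation to be reported. A site that defers the first charge because staples are in place cannot tell from the CIP whether it has deviated. SAP 3.3 summarises deviations by category, so sites could report the same conduct differently.
- **Reading the charging data.** SAP 3.4 summarises the days from implant to first charge. A deferral because of staples would lengthen that time, and no data item listed in the CIP records the reason.

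**Working it through.** The documents give no figure to reproduce. The check is a comparison of the text plus the visit window.

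1. **Inputs.** Let V be the day of the 2-week visit, F the day of the first charge and S the day the staples come out, all counted from implant. CIP 6.3.1 gives 10 ≤ V ≤ 14. Neither document gives S or says whether staples are used.

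2. **Charging-plan criterion (CIP 6.2).** F must come before the visit at V. No earliest day is set. F therefore lies between day 0 and, at the latest, day 10 to day 14, depending on when the visit takes place.

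3. **Staple warning (CIP 15.2).** If staples were used, F must not come before S.

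4. **Both together.** A permissible F exists only if the staples are out before the visit. Without staples, or with staples out in time, both statements can be met. If staples are still in place up to the visit, no day satisfies both. For a visit on day 10 the conflict arises if staples remain up to day 10; for a visit on day 14, if they remain up to day 14.

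5. **Does the wound-healing clause resolve it?** The clause in CIP 6.2 attaches healing to weekly charging, and the second criterion starts weekly charging after 2 weeks. The first charge is a separate criterion that falls earlier. The clause does not reach it on its wording.

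6. **Does a scheduled check resolve it?** In the Schedule of Events (CIP 6.3.5) the columns after the implant procedure are the 2-week visit, the 6-week visit and unscheduled visits. No row covers a wound or staple check at any visit. Unscheduled visits (CIP 6.3.4) are driven by events. CIP 6.2 allows activation and programming at an office visit, which could precede the first charge, but attaches no wound or staple check to it. The 2-week visit comes after the charge is due and may be by telephone.

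7. **Size.** With S unknown, the affected share of implanted subjects is between 0% and 100%, that is, 0 to 20 of the planned 20. The documents do not allow a narrower range.

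**The case against.** The strongest reply is that the two sections are compatible on their face. Both say *should*, not *must*. The first charge has no earliest day, and CIP 6.2 speaks of a plan for the individual patient, set with instruction from the investigator or delegate, which leaves room to apply the staple precaution. A site that follows the whole CIP has the warning in hand. The IFU, which carries it, is not among the documents, and neither are the case report forms or the consent form; CIP 10.4.1 also requires training on device use. Most of this stands. It makes the conflict conditional and means that its frequency is not shown. It does not remove the gap, because meeting both statements depends on a condition that the CIP neither states nor checks.

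A reader might also infer more than the text supports:

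- *That every subject is made to charge over staples.* The documents do not say that staples are used, and a subject without them meets both statements.
- *That the day 10-14 visit is the first contact after implant.* Activation may take place at an earlier office visit, and a CIP activity schedule does not show that routine wound care is absent. The supportable statement is that the CIP links no such check to the first charge.
- *That counting a staple-heating event as charging-related would distort the confirmatory endpoint.* Such an event would be charging-related, so counting it would be correct classification. It would also have to meet the seriousness criteria in CIP 7.1.2 and be adjudicated as related to enter that endpoint; CIP 15.2 names only heating or discomfort.
- *That the conflict can be sized by what one more serious event does to the confidence interval.* That shift follows from any single related serious event in a study of this size and does not measure this conflict.

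**Conclusion.** The point holds in conditional form. As written, the first-charge criterion in CIP 6.2 and the staple warning in CIP 15.2 cannot both be followed for a subject whose staples are still in place when the charge falls due, and nothing in the CIP rules that case out. The number of such subjects is unknown and may be zero.

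The conclusion assumes that the wound-healing clause applies to weekly charging only, as its wording indicates, and that no unseen document ties the first charge to staple removal. If the IFU or site procedures already do so, the practical risk is smaller, but the CIP text still needs to agree with them. The sections should be corrected because the matter concerns safe use of the component under study and the correction is cheap. It does not call the confirmatory analysis into question. No view is taken on which charging statement is right.

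**What to change.** Reconcile CIP 6.2, 6.3.1 and 15.2 so that the first-charge criterion and the staple warning cannot conflict for any subject. State in the same text whether deferring the first charge because of staples counts as a CIP deviation. Which statement governs, and on what terms, is for the sponsor and investigators.

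Optionally, if the case report form does not already do so, record whether staples were in place at the first charge. This would give context for charging events and for the SAP 3.4 summary of time to first charge.

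The cost is minor CIP wording. Because the text concerns subject care, CIP 10.3 may call for ethics committee approval and not only notification. The optional field adds a small amount of site work.
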